3.3 SECONDARY ENDPOINTS ANALYSIS

Secondary **efficacy** endpoints analyses are defined in this section.

Secondary **safety** endpoints analyses are defined in [Section 3.6.2](#) (AE, serious AE [SAE], AE of special interest [AESI]) and [Section 3.6.3](#) (clinical safety laboratory variables, vital signs, and electrocardiogram [ECG]).

The main analysis approach for the secondary efficacy endpoints will be to analyze the endpoints on the mITT population, ie, all enrolled participants who received at least 1 dose of IMP and with an ADAMTS13 activity of <10% at baseline.

Secondary endpoints listed below will be analyzed using the count and percentage of participants. Two-sided 95% CIs will be provided.

- Proportion of participants achieving remission during the overall study period.
- Proportion of participants who require TPE during the on-treatment period.
- Proportion of participants achieving Clinical Response during on-treatment period and during the overall study period.
- Proportion of participants refractory to therapy during the on-treatment period.
- Proportion of participants with iTTP-related death during the on-treatment period and during the overall study period.
- Proportion of participants with a clinical exacerbation of iTTP during the on-treatment period and during the overall study period.
- Proportion of participants with a clinical relapse of iTTP during the on-treatment period and during the overall study period.

For the following time to event endpoint, median time to event (with 2-sided 95% CI) as well as Q1 and Q3 will be estimated using Kaplan-Meier estimates, and survival curve provided.

- Time to platelet count response, defined as time from start of treatment to initial platelet count $\geq 150 \times 10^9/L$ that is sustained for ≥ 2 days.

[figure not shown]
The percentage of event at the following timepoints during the on-treatment period, will be also provided: Day 1, Day 2, Day 3, Day 4, Day 5, Week 1, Week 2, Week 3, Week 4, Week 8, and Week 12.

[figure not shown]
More details regarding the definition and derivation of these endpoints are provided in [Section 5.4](#).

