 - If only 1 local result is available with same date, the local result will be used to impute central value
 - If multiple local records are available:
 - If central and local records have date and time, the local record with the closest sample time to the missing central record will be used
 - If central record has only sample date and not sample time, the **median** value from the local samples on the same date will be used to impute the missing central record.
 - If duplicates of central records with same date, time and results, only one record will be kept
 - If for the same date and time, one record is “NOT DONE” and one record has a result, the record with the result will be kept
 - In case of missing CENTRAL record for platelet, LDH, cTnI and creatinine (reported as “NOT PERFORMED” in the rawdata), the missing record will be replaced according the following rule (in this order):
 - If a local record is available with matching sample visit, the local result will be used to impute central value
 - If multiple local records are available:
 - the **median** value from the local samples on the same visit will be used to impute the missing central record.
 - If multiple central records are available for the same date, the median value from the central values will be used.
 - For ADAMTS13 activity if a central sample was not done, then a local value, if available, can be substituted for the particular missing value.
 - For antibody titers, only central assessments will be used.

Then, and only after the potential above imputations, to derive the efficacy derived endpoints concerning platelet, LDH, cTnI and creatinine parameters (like Remission, Clinical response, Refractory to therapy, Clinical Relapse, Clinical exacerbation, Time to ...), only 1 unique value per day will be retained; this one will correspond to the median value observed among all values recorded on the following time windows:

- [0-24h] according to the actual elapsed time from first dose (1st administration of caplacizumab, whether is the marketed caplacizumab as first dose within 4 hours prior to enrollment or first dose of IMP, and whether the first dose is intravenous or subcutaneous administration, ie, ignoring route of administration for calculation of actual elapsed time from first dose)
- [>24-48h]
- [>48-72h]
- And for the following days >3, by calendar day.

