- The values resulting from these derivations will be the values used for the graphical representation of platelet, LDH and ADAMTS13 activity from Day 4.

Consecutive laboratory assessments are considered as 'consecutive visits' for efficacy endpoints.

A participant could potentially have missing laboratory assessment data, however, remission could still be confirmed at a subsequent laboratory value. In the case there is inadequate information to determine the remission status of a participant by the end of the study, the participant will be treated as not having achieved remission.

Clinical evidence of new or progressive ischemic organ injury

Clinical evidence of new or progressive ischemic organ injury is defined as any presence of following clinically significant iTTP event:

- Neurological event
- Elevated cardiac troponins
- Acute myocardial infarction
- Conduction abnormality
- Repolarization abnormality
- Heart failure
- Clinically significant renal event

which will be identified from the checkboxes in the "Clinically Significant TTP Event" eCRF form.

Exacerbation of TTP, Relapse of TTP and Other event will not be considered as clinical evidence of new or progressive ischemic organ injury.

Sustained Clinical Response

Sustained Clinical response is defined by the concomitance of the 3 following criteria for at least 2 consecutive visits (starting from D2):

- platelet count $\geq 150 \times 10^9/L$
- LDH $< 1.5 \times ULN$
- no clinical evidence of new or progressive ischemic organ injury

Remission

Remission is defined as (1) a sustained Clinical response (see above) associated with (2) Clinical remission or (3) Complete ADAMTS13 Remission, whichever occurs first, and defined as:

- Clinical remission: No TPE (*Plasma Exchange* form) and no anti-VWF therapy (Caplacizumab treatment) for ≥ 30 days (from the date that Clinical Response is achieved).
- Complete ADAMTS13 Remission: The attainment of ADAMTS13 activity level $\geq 50\%$ for at least 2 consecutive visits (starting from D2).

Time to event

For each of below time to event, in case of no observation of the event or death, the censoring date will be defined as the last non-missing value of the analyzed parameter (platelet count, LDH....) if any, else as the start date of treatment (defined as first caplacizumab administration [whatever marketed or study IMP]).

- Time to platelet count response will be calculated as follow:

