Date of initial day of 2 consecutive days where platelet count $\geq 150 \times 10^9/L$ - Date of start of treatment

- Time to LDH $\leq 1 \times$ ULN will be calculated as follow:
Date where LDH $\leq 1 \times$ ULN for the first time - Date of start of treatment
- Time to serum creatine $\leq 1 \times$ ULN will be calculated as follow:
Date where serum creatine $\leq 1 \times$ ULN for the first time - Date of start of treatment
- Time to cardiac troponin I $\leq 1 \times$ ULN will be calculated as follow:
Date where serum creatine $\leq 1 \times$ ULN for the first time - Date of start of treatment
- Time to ADAMTS13 partial remission (ADAMTS13 activity between 20% [included] and lower limit of normal [LLN] [excluded]) at 2 consecutive visits after clinical response will be calculated as follow:
Date of initial day of 2 consecutive visits after clinical response with ADAMTS13 partial remission - Date of start of treatment
- Time to normalization of ADAMTS13 level defined as sustained ADAMTS13 level of $\geq 50\%$ at 2 consecutive visits after clinical response will be calculated as follow:
Date of initial day of 2 consecutive visits after clinical response with normalization of ADAMTS13 level - Date of start of treatment
- Time to reduction of anti-ADAMTS13 antibodies below the threshold of positivity (12 U/mL) will be calculated as follow:
Date of reduction of anti-ADAMTS13 antibodies below the threshold of positivity - Date of start of treatment

Refractory to therapy

Refractory to the therapy during the on-treatment period is defined as following:

- Lack of platelet count increment (over 2 consecutive days),
OR
- platelet counts $<50 \times 10^9/\text{L}$ AND LDH $>1.5 \times \text{ULN}$ despite 5 days of treatment.

Note: if the 2 consecutive values of platelet are the same, the condition is not met for refractory. Additionally, a patient can become refractory after a sustained platelet count response if he still is on therapy.

iTTP-related death during the on-treatment period and during the overall study period

The iTTP-related deaths will be derived from the ***Clinically Significant iTTP Event*** form with the ***Outcome*** field filled as Fatal.

Clinical Exacerbation

Clinical exacerbation is defined between a Clinical Response and a Clinical Remission as:

- platelet count decreases to $<150 \times 10^9/\text{L}$ (note that it is assumed that other causes of thrombocytopenia are excluded from the data collected in the database),

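### SAP 5.4 dates cardiac troponin I normalisation from serum creatinine, a copy error; a lesser gap is that the two-consecutive-day platelet rule is not defined for weekly outpatient counts

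*SAP*

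**What the plan says.** **Troponin.** The time-to-event list in SAP 5.4 has separate entries for serum creatinine and for "Time to cardiac troponin I", each with a threshold of 1 × ULN. Both have the same formula beneath them: "Date where serum creatine" (evidently creatinine) first reaches the limit, minus the start of treatment.

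**Platelets.** SAP 3.3 lists "Time to platelet count response, defined as time from start of treatment to initial platelet count" of at least 150 × 10⁹/L, sustained for at least 2 days. SAP 5.4 turns this into "Date of initial day of 2 consecutive days where platelet count" meets the threshold. Four other rules in SAP 5.4 bear on it:

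- One value per day is kept: the median within 24-hour windows up to 72 hours, then "for the following days >3, by calendar day".
- "Consecutive laboratory assessments are considered as" consecutive visits for efficacy endpoints. The rule does not mention consecutive days.
- The refractory definition uses consecutive days, but its note considers what happens "if the 2 consecutive values of platelet are the same".
- With no event, "the censoring date will be defined as the last non-missing value of the analyzed parameter".

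**Schedule.** Platelets are counted daily in hospital (Protocol 1.3.2) and weekly, ±3 days from Day 8, after discharge (Protocol 1.3.3 and 4.1). Protocol 4.1 does not fix the length of stay.

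**The concern.** Followed as printed, the troponin derivation would give creatinine event dates under a troponin title.

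For platelets, two programmers could classify the same late responder differently. One would require counts on adjacent days, find none once sampling is weekly, and censor. The other would accept the next available count and record an event. On the first reading, a participant could meet the platelet criterion for Clinical Response, which is judged on consecutive assessments, yet have no platelet count response. That would affect the Kaplan-Meier curve and the event percentages that SAP 3.3 requests as far as Week 12.

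**Working it through.** **1. Troponin, by comparing the text.** The creatinine and troponin entries have different labels and identical formulas. Nothing else in the visible SAP dates the troponin event from troponin. The censoring rule refers to the parameter being analysed. Followed literally, events would therefore come from creatinine and censoring from troponin, which is not coherent. No arithmetic is needed.

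**2. Gaps between platelet counts** (visit windows from Protocol 1.3.3 and 4.1)

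- Successive weekly visits: 7 ± (3 + 3) = 1 to 13 days.
- One weekly visit missed: 14 ± 6 = 8 to 20 days.
- Follow-up Day 7 to Day 28: 21 ± (1 + 1) = 19 to 23 days. Participants whose ADAMTS13 activity is below 50% when caplacizumab stops have extra visits at Days 14 and 21.
- Follow-up Day 28 to Week 12: 56 ± (1 + 3) = 52 to 60 days.

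Two successive weekly visits fall on adjacent days only if the first is 3 days late and the second 3 days early. That is 1 of 7 × 7 = 49 whole-day combinations.

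**3. How often the literal rule misses a late responder.** Assumptions, none of them from the documents: all later counts are normal, visit offsets are uniform and independent over −3 to +3 days, and there are no unscheduled samples. Weekly visits run from Day 8 to at most Day 78 (SAP Table 7), so there are at most (78 − 8)/7 + 1 = 11. Treatment length varies, so 4 and 11 visits are shown.

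Let N(k) be the number of offset sequences for k visits that contain no adjacent-day pair. Then N(k) = 7·N(k−1) − N(k−2), with N(0) = 1 and N(1) = 7. This gives N(3) = 329, N(4) = 2,255, N(9) = 34,111,385, N(10) = 233,802,911 and N(11) = 1,602,508,992.

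*Case A: first count of at least 150 on the last inpatient day (Day 4 to 7).*

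- Correct date (first weekly visit is the next day): 1/7 = 14.3%.
- No event, [N(k) − N(k−1)]/7^k: 1,926/2,401 = 80.2% with 4 visits; 1,368,706,081/1,977,326,743 = 69.2% with 11.
- Event dated too late (the remainder): 5.5% to 16.5%.
- If the first weekly visit must follow discharge, the no-event range over Days 4 to 7 and 4 to 11 visits is 59.1% to 80.2%. The low end is Day 7 with 11 visits: [3·N(10) − N(9)]/(4 × 7^10) = 667,297,348/1,129,900,996 = 59.1%.

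*Case B: first count of at least 150 at the first weekly visit.*

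- Correct date: 1/49 = 2.0%.
- No event, N(k)/7^k: 2,255/2,401 = 93.9% with 4 visits; 1,602,508,992/1,977,326,743 = 81.0% with 11.
- Event dated too late: 4.0% to 16.9%.

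These chances apply only to someone who is already such a late responder. They do not say how often that happens.

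**4. Effect on the reported percentage.** One participant is 1/55 = 1.8 points (SAP section 4) or 1/30 = 3.3 points (interim, SAP 3.8). The documents do not give the number affected, so a range is assumed:

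| Affected | n = 55 | n = 30 |
|---|---|---|
| 0 | 0 | 0 |
| 1 | 1.8 points | 3.3 points |
| 2 | 3.6 points | 6.7 points |
| 3 | 5.5 points | 10.0 points |

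If everyone else responds, the Week 12 event percentage at n = 55 would be 98.2%, 96.4% or 94.5% for 1, 2 or 3 affected.

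**The case against.** The troponin label states the event plainly, and SAP 5.4 treats troponin as its own parameter when retaining daily values. A careful programmer would notice the conflict. That stands: a reader might infer that the troponin results will be wrong, but the documents support only that the formula is wrong as printed.

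On platelets, the refractory note moves from days to values, which suggests that the authors meant successive retained values. That makes the benign reading plausible, but it does not settle the matter. The same time-to-event list uses consecutive days for platelets and consecutive visits for ADAMTS13, and the bridging rule names only visits.

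The number affected may well be zero. Protocol 2.3.2 cites a case series in which platelets normalised in 48 to 96 hours, and platelet recovery within 5 days in all 11 published episodes treated without TPE. Counts are daily in hospital, and participants on TPE continue daily exchange for at least 2 days after normalisation. Unscheduled samples could also supply a second count. All of this stands.

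A reader might infer from the 59% to 94% figures that many participants would be lost, that the Kaplan-Meier median would be distorted, or that the primary result is at risk. The documents support none of these. The figures are conditional, the median does not move if more than half respond in hospital, and the primary endpoint uses consecutive assessments.

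**Conclusion.** The troponin formula is wrong as written and should be corrected. Its practical impact is small, because the intent is plain and the endpoint is not a listed primary or secondary one.

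The platelet rule is a minor under-specification of a secondary endpoint. It matters only on the literal reading, and only for participants whose first normal count falls on or after the last daily inpatient count. On that reading such a participant would usually be censored, given the uniform-offset assumption and no extra samples. The cost of 1.8 points each at n = 55 (3.3 at n = 30) assumes no other censoring before the timepoint reported. All analyses are descriptive, and sample size is not affected.

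**What to change.** 1. In the troponin entry, replace the creatinine date with the first date on which cTnI is at or below 1 × ULN.

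2. Define platelet response as the first retained value of at least 150 × 10⁹/L that is confirmed by the next retained value, on a later day, also at least 150 × 10⁹/L. Date the event at the first value.

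3. State a maximum gap between the two values, chosen by the sponsor. For example, 13 days covers two on-schedule weekly visits but fails after many single missed visits (8 to 20 days). A limit of 20 days allows one missed weekly visit, but overlaps the 19 to 23 days between the Day 7 and Day 28 follow-up visits.

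4. Say what a later day means at the 72-hour switch from elapsed-time windows to calendar days. After an evening first dose, a Day 4 morning sample falls both in the third window and on calendar Day 4.

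Where daily inpatient counts are complete, results are unchanged apart from that boundary. The downside is that a dip between weekly samples goes unseen. The cost is a few SAP sentences and the matching programming; no new data are needed.

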4 STUDY DESIGN

4.1 OVERALL DESIGN

This is a single-arm, open-label, Phase 3, multicenter study to evaluate the efficacy and safety of caplacizumab and IST without first-line TPE in adult patients with an acute episode of iTTP.

This study incorporates the revised consensus outcome definitions for iTTP published by the International Working Group for TTP that reflect current iTTP management (3). A Data Monitoring Committee will be appointed to monitor the safety and scientific integrity of this study.

Participants will be recruited from sites that are able to obtain baseline ADAMTS13 activity test results within 2 days (48 hours) and provide TPE services, overnight and during weekends if needed.

Adult participants will be enrolled based on a clinical diagnosis of iTTP (initial or recurrent). Those with thrombocytopenia (defined as platelet count $<100 \times 10^9/L$) and who have evidence of microangiopathic hemolytic anemia (eg, presence of schistocytes in peripheral blood smear) and relatively preserved renal function are considered to have a clinical diagnosis of iTTP. In addition, we will use the French TMA Score, a clinical scoring system that predicts severe ADAMTS13 deficiency (29) to further establish the clinical diagnosis. A French TMA score of 2 (platelet count $\leq 30 \times 10^9/L$ and serum creatinine $\leq 2.27 \text{ mg/dL}$) is considered highly suggestive of iTTP. Those with a French score of 1 (either platelet count $\leq 30 \times 10^9/L$ or serum creatinine $\leq 2.27 \text{ mg/dL}$) will be considered having probable iTTP.

After confirmation of eligibility to participate in the study, the enrolled participants will undergo baseline laboratory studies including ADAMTS13 activity level.

The initial treatment regimen consists of caplacizumab and IST (corticosteroids \pm anti-CD20 antibody [rituximab or biosimilar]) without first-line TPE. Those participants with a clinical diagnosis of iTTP and a French score of 1 or 2, will be started on treatment with Caplacizumab and corticosteroids immediately pending the availability of baseline ADAMTS13 activity level from the local laboratory. It is important to note that the baseline ADAMTS13 activity results will be available within 48 hours. It is recommended that participants start anti-CD20 antibody therapy after confirmation of diagnosis of iTTP ($<10\%$ ADAMTS13 activity).

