- If the baseline central laboratory ADAMTS13 activity is >20% of normal → **Caplacizumab therapy should be discontinued**, and other diagnoses should be considered. Please see [Section 7](#) of the protocol for additional details.

2. Immunosuppressive therapy:

- Corticosteroid therapy: It is expected that all participants will receive corticosteroids. Recommended dose: Prednisone or Prednisolone 1.0-1.5 mg/kg/day, IV or oral, for 1 week and taper over 3 to 4 weeks based on institutional guidelines. The dose and duration of therapy may be adjusted as clinically indicated.

- Anti-CD20 antibody therapy (rituximab or biosimilar): Recommend starting anti-CD20 antibody therapy at the beginning of the study, once iTTP diagnosis is confirmed (ADAMTS13 activity level <10%) and is required if ADAMTS13 activity level remains <10%, 1 week after platelet count normalization or stop of TPE (if TPE was started)

Recommended dose:

375 mg/m² IV infusion (as per instructions on package insert) × 3-4 doses once a week or as per institutional guidelines.

Note:

If there is inadequate response to the initial IST regimen (corticosteroids with or without anti-CD20 antibody therapy) and ADAMTS13 activity level remains <10% after 4 weeks of therapy, the Investigator may consider optimizing IST further (including adding anti-CD20 antibody if not done before) or consider alternative immunosuppressive therapies as per local standard of care.

Therapeutic Plasma Exchange (TPE):

After the first 24 hours of treatment (cplacizumab + IST) (or during the first 24 hours per the judgement of the investigator if there is any evidence of clinical deterioration, as explained below), TPE may be started under the conditions listed below. Initial response to therapy will be evaluated based on laboratory data obtained during the first 24-hours including those performed at the 24-hour timepoint. However, please note that the platelet response is expected within the first 6 to 12 hours based on previously published data (2).

Cplacizumab and IST will be continued after starting TPE.

TPE may be started:

- If there is no initial response to therapy defined as absence of increase from baseline in platelet counts (over at least 2 consecutive values) and absence of decrease from baseline in LDH (at least 2 consecutive values) after 24 hours of treatment.

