- If there is persistent thrombocytopenia, defined as lack of a sustained platelet count increment or platelet counts of $<50 \times 10^9/L$ and a persistently raised LDH level ($>1.5 \times$ upper limit of normal [ULN]) despite five days of treatment.
- If there is clinical evidence of new or progressive ischemic organ injury (worsening of presenting signs and symptoms or appearance of new signs and symptoms such as but not limited to neurologic manifestations [seizures, sudden onset numbness or weakness of the face, arm, or leg especially on one side of the body, mental status changes including confusion, trouble speaking, or understanding speech, sudden visual impairment, sudden difficulty walking, loss of balance or coordination, sudden severe headache with no known cause], cardiac manifestations such as chest pain with or without electrocardiogram (ECG) changes suggestive of myocardial ischemia, increasing troponin, renal manifestations such as worsening serum creatinine at any time after starting therapy, TPE may be started at Investigator discretion at any point during the study, including the first 24 hours and cplacizumab and IST continued.

If participant needs TPE:

Recommend TPE with plasma (eg, fresh frozen plasma, solvent detergent/viral-inactivated plasma, cryosupernatant) at 1 to $1.5 \times$ estimated plasma volume. TPE should be performed daily according to standard site practice and continued at least for 2 days after the platelet count normalization ($\geq 150 \times 10^9/L$). Of note, TPE with 1 to $1.5 \times$ estimated plasma volume may be spread over multiple sessions within 24 hours. Tapering of TPE after platelet count normalization, defined as reducing its frequency to less than once per day, is strongly discouraged and if considered, should be discussed with the Medical Monitor.

Treatment plan for continued therapy with cplacizumab and IST regardless of hospitalization status:

If there is response to initial therapy:

- The participant will continue cplacizumab 10 mg (11 mg in US and Canada) SC daily until sustained ADAMTS13 normalization ($\geq 50\%$) at 2 consecutive visits after platelet count normalization defined as $\geq 150 \times 10^9/L$, or for 12 weeks, whichever occurs first. The maximum treatment duration of cplacizumab is 12 weeks for the presenting episode.

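### The SAP rule for refractory disease has a first branch with no reference value and no 5-day, low-count or LDH condition, so as laid out it can count responders and early recoverers as refractory.

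*SAP*

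**What the plan says.** The endpoint is defined in one sentence, the same in Protocol Table 2 and SAP Table 1. It joins a lack of *sustained* platelet increment over 2 consecutive days, by *or*, to counts below 50 x 10^9/L and persistently raised LDH, and it ends with the 5-day condition. It has no brackets, so the 5-day and LDH conditions could govern both limbs or only the second.

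SAP section 5.4 (Refractory to therapy) turns the sentence into two bullets joined by OR:

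- First: "Lack of platelet count increment (over 2 consecutive days"). The word *sustained* is gone.
- Second: platelets below 50 x 10^9/L and LDH above 1.5 x ULN after 5 days of treatment.

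Two remarks follow: "if the 2 consecutive values of platelet are the same, the condition is not met for refractory", and "Additionally, a patient can become refractory after a sustained platelet count response if he still is on therapy".

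The same appendix says that "Sustained Clinical response is defined by the concomitance of the 3 following criteria for at least 2 consecutive visits", from Day 2: platelets at least 150 x 10^9/L, LDH below 1.5 x ULN, and no new or progressive ischemic organ injury. Consecutive laboratory assessments count as consecutive visits. One platelet value per day is kept. The first three daily windows run to 24, 48 and 72 hours from the first dose, and later days are calendar days.

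Protocol section 4.1 shows that a reference value can be stated: its 24-hour criterion for starting TPE is "absence of increase from baseline in platelet counts (over at least 2 consecutive values"). A separate TPE criterion uses wording close to the endpoint: "If there is persistent thrombocytopenia, defined as lack of a sustained platelet count increment or platelet counts of" below 50 x 10^9/L with raised LDH after five days.

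**The concern.** Refractory disease is one of the outcomes that bears directly on whether first-line TPE can be left out. A rule that omits what the increment is measured against, and attaches the qualifying conditions to only one of its two branches, can be programmed in several ways from the same text. On some of them the count would include participants who are doing well. The same two platelet values could then feed both the Clinical Response proportion and the refractory proportion, which a reader would take as opposite outcomes. With 55 participants in the mITT population, each misclassified participant moves the proportion by 1/55 = 1.8 percentage points.

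**Working it through.** The documents give no expected refractory rate, so there is no figure to reproduce. The check applies the rules to short platelet series (x 10^9/L).

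**1. What the increment is compared with.** The first bullet does not say. Two equal values also lack an increment, so excluding them makes most sense if each value is compared with the one before it. Against baseline the exclusion would be odd: baseline 20 followed by 18 and 18 would be exempt, while 18 and 17 would count. The second remark lets the event follow a sustained response, so normal counts are not excluded. The text points to a previous-day comparison but does not state one.

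**2. Overlap with Clinical Response.** Take 310 then 300 on consecutive on-treatment days from Day 2, LDH 1.0 x ULN, no organ injury.

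| Reading of the first branch | Clinical Response | Refractory |
|---|---|---|
| Previous-day reference, two values | met | met |
| Previous-day reference, 5-day condition on both branches, pair after Day 5 | met | met |
| No rise on each of two days (three values) | met | not met by this pair alone |
| Baseline reference | met | not met |
| LDH condition on both branches | met | not met |

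With LDH on both branches the overlap is impossible: the same values cannot be both below and above 1.5 x ULN. With a baseline reference it practically disappears. Protocol section 4.1 describes eligible patients as "Those with thrombocytopenia (defined as platelet count" below 100 x 10^9/L), and exclusion E 01 removes counts of 100 or more. A response value is at least 150, so it could fail to exceed baseline only if baseline were itself 150 or more.

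**3. Early dip.** Take baseline 20, daily values 18 then 17, and a normal count by Day 4.

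- Previous-day reference: 17 < 18, so the first branch is met.
- Baseline reference: 18 < 20 and 17 < 20, so it is met.
- 5-day condition on both branches: not met.

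The two values come from the first two windows, the second of which closes at 48 hours. Five days is 5 x 24 = 120 hours. The 48 hours is the end of that window, not an earliest time: samples are scheduled at 24 (±2), 30 and 36 hours, so the second value may rest on blood drawn soon after 24 hours. A three-value reading that did not count baseline would use the third window, which closes at 72 hours, still short of 120.

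**4. Illustration of size.** Assume independent lognormal noise with coefficient of variation CV and true growth r per day. Let s = sqrt(ln(1 + CV²)). Then P(one pair falls) = Φ(−ln(1 + r) / (s√2)). For three values, P(both steps fall) is the bivariate normal probability that two differences, each with mean ln(1 + r) and variance 2s² and with covariance −s², are both negative.

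| Growth per day | One pair falls (CV 5% to 8%) | Both steps of a triplet fall (CV 5% to 8%) |
|---|---|---|
| 0% | 50% | 16.7% (= 1/3!) |
| 2% | 39% to 43% | 7.7% to 10.5% |
| 10% | 9% to 20% | 0.05% to 0.8% |

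For example, r = 2% and CV = 5% give s = 0.0500, ln(1.02) = 0.0198, and Φ(−0.0198 / 0.0707) = Φ(−0.280) = 0.390.

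These are chances for one pair or one triplet. They accumulate over daily counts: for m stable values the chance of at least one fall is 1 − 1/m!, or 83.3% for m = 3. The number of daily counts after recovery depends on length of stay, which the documents do not give. CV, growth and independence are assumptions.

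**The case against.** The strongest reply is that the endpoint sentence in Protocol Table 2 and SAP Table 1 keeps *sustained* and ends with the 5-day condition, which can naturally govern both limbs. Read that way, the early-dip problem goes away. This is a fair reading of the sentence, but section 5.4 is the derivation that will be programmed, and its layout puts the condition in the second bullet only. Even with the 5-day condition on both branches, two falling normal counts after Day 5 would still qualify on the previous-day reading.

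A second reply is that two consecutive days may mean no rise on each of two days, which needs three values and lowers the probabilities considerably, as the table shows. That reading is possible, but the tie remark speaks of two values.

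A third reply is that the mix of *days* in the bullet and *values* in the remark is not a real ambiguity, because one value per day is kept for this endpoint. That stands: two values most simply means two daily values, and I make no separate point of it.

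A reader might go further and infer that the SAP definitely counts responders as refractory, that the refractory rate will be heavily inflated, or that the primary result is compromised. The documents support none of these. The reference value is unstated, not fixed at the previous day; the number of inpatient days after recovery is unknown; and the primary endpoint does not use this rule. Nor does the SAP derivation trigger TPE, which follows the protocol's own criteria.

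**Conclusion.** The point holds as a defect in one derivation rule, and it should be fixed. As laid out, the first branch lacks a reference value and any 5-day, low-count or LDH condition. Two consequences follow, each with its own condition:

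- A participant can meet both Clinical Response and refractory if consecutive values are compared with each other. This is the reading the remarks suggest, but it is not explicit. The overlap is impossible with LDH on both branches and practically absent with a baseline reference.
- A participant with a dip in the first 48 hours who recovers by Day 4 can be counted with either reference, unless the 5-day condition governs both branches.

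The effect on the reported proportion cannot be estimated from the documents, and the probabilities above rest on assumed noise and growth. The reach is limited to one secondary proportion and its 95% CI, in the mITT population and again in the FAS. All analyses are descriptive, with no success criterion. Confidence is medium because the outcome turns on an unstated reference.

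**What to change.** Reconcile the derivation in SAP section 5.4 with the endpoint definition in Protocol Table 2 and SAP Table 1, and check it against the similar wording in Protocol section 4.1. Rewrite it so that a day-to-day fall between normal counts cannot by itself classify a participant as refractory. The revised text should:

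1. state the reference value for the increment;
2. state how many daily values are needed;
3. show with explicit brackets which branches the 5-day condition and the LDH condition govern;
4. align the remark on refractoriness after a sustained response with the reconciled rule.

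The clinical definition is the sponsor's choice; the request is only that it be stated so that it can be programmed in one way. The cost is SAP wording and programming. No new data, visits or participants are needed.
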